9.4 Cardiovascular Assessment

9.4.1 Cardiovascular Analyses

The primary parameters for the cardiovascular analyses will be peak hourly mean values of SBP, diastolic blood pressure (DBP), and mean arterial pressure (MAP), and nadir hourly mean values for pulse rate (PR), and will be determined by ambulatory blood pressure monitoring (ABPM). These data will be listed and summarized by treatment.

Mean hourly SBP, DBP, MAP, and PR values will be calculated, summarized by treatment, and plotted, together with changes from baseline. Baseline value will be defined as the mean value during the 2 hours pre-dose for each period.

Finally, descriptive statistics will be used to summarize the mean values of SBP, DBP, MAP, and PR parameters over the intervals 0-4 h, 4-8h, 8-12 h, and 12-24 h.

9.4.2 Cardiovascular Statistical Methodology

Primary analysis

Changes from baseline in peak hourly mean values of cardiovascular parameters SBP, DBP, and MAP, and nadir hourly mean values of PR will be analysed to determine the impact of a single dose of sumatriptan 100 mg on the peak/nadir hourly mean values of the cardiovascular parameters of lasmiditan. A linear mixed-effects model with baseline as a covariate, fixed effects for treatment, period (1, 2, 3, or 4), and treatment sequence, and a random effect for subject will be used. Least squares (LS) means and treatment differences ($[\text{lasmiditan} + \text{sumatriptan}] - [\text{lasmiditan} + \text{placebo}]$) will be calculated and presented with the corresponding CIs.

Primary cardiovascular parameters may be log-transformed prior to the statistical analysis if a review of the data indicates that the assumption of normality is violated.

The same model will be used to assess the impact of a single dose of lasmiditan 200 mg on the peak/nadir hourly mean values of the cardiovascular parameters of sumatriptan.

An example of the SAS code that will be used is as follows:

```
proc mixed data=xxx;  
  class trtmnt period seq subject;  
  model primcard = base trtmnt period seq / alpha=0.1 cl ddfm=kr;  
  random subject;  
  lsmeans trtmnt / alpha=0.1 cl pdiff;  
run;
```

where 'primcard' is the change from baseline in the peak/nadir hourly mean values of the primary cardiovascular parameters SBP, DBP, MAP/PR respectively.

Repeated measures analysis:

Changes from baseline in cardiovascular parameters will be evaluated to determine the impact of a single oral dose of sumatriptan 100 mg on the cardiovascular parameters of single oral dose of lasmiditan 200 mg.

A repeated measures linear mixed-effects model with baseline as a covariate, fixed effects for time point, treatment, period (1, 2, 3, or 4), treatment sequence, and the treatment by time point interaction, and a random effect for subject will be used. LS means and treatment differences ([lasmiditan + sumatriptan] – [lasmiditan + placebo]) will be calculated and presented with the corresponding 90% CIs.

An example of the SAS code that will be used is as follows:

```
proc mixed data=xxx;  
  class trtmnt subject time period seq;  
  model cardio = base time trtmnt period seq trtmnt*time / alpha=0.1 cl ddfm=kr;  
  repeated time / type=un subject=subject;  
  random subject;  
  lsmeans trtmnt*time / alpha=0.1 cl pdiff;  
run;
```

where 'cardio' is the change from baseline in the cardiovascular parameter.

Cardiovascular parameters may be log-transformed prior to the statistical analysis if a review of the data indicates that the assumption of normality is violated.

The same model will be used to assess the impact of a single dose of lasmiditan 200 mg on the cardiovascular parameters of sumatriptan.

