7.2.1. Timing of Doses

The doses will be administered at approximately the same time on Day 1 of each treatment period. The actual time of all dose administrations will be recorded in the subject's electronic case report form (eCRF).

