9.4.2.2. Ambulatory Blood Pressure Monitoring

For each subject, ABPM will be performed according to the Schedule of Activities (Section 2).

Site investigative personnel should be trained on the correct positioning of the ABPM monitor, use of correct cuff size, and monitor calibration prior to the start of the study. Subjects should be trained on the ABPM device before the predose measurement in the first treatment period to maximize the collection of valid measurements, and to alleviate any concerns about inconvenience due to the continuous 24-hour monitoring.

The ABPM device should be attached to the subject's nondominant arm and will record ambulatory BP and PR every 20 minutes during awake hours (for example, 0700 hours to 2200 hours) and every 30 minutes throughout the night (2200 hours to 0700 hours). On Day 1 of each treatment period, the BP and PR recording will be initiated approximately 2 hours prior to the planned dosing time and will continue for approximately 26 hours. Subjects will be encouraged to keep the same routine without strenuous activity during the ABPM recording days.

The ABPM device should be removed from each subject prior to their discharge from the CRU.

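### The hourly repeated-measures model has no subject-by-time term and its example code cannot be fitted; the usual repair would leave the hourly A-B and A-C 90% CIs conservative if subjects' hourly profiles recur across periods

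*SAP*

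**What the plan says.** SAP 9.4.2 has two cardiovascular models. The primary one takes a single peak or nadir change per subject and period, with baseline, treatment, period, sequence and a random subject effect. The second, the subject of this point, is a repeated-measures model for the changes over time. Its prose lists baseline, time point, treatment, period, "treatment sequence, and the treatment by time point interaction, and a random effect for subject will be used". Protocol 10.3.3.2 has the same prose and no code.

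The SAP adds example code for the second model:

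- fixed part: "model cardio = base time trtmnt period seq trtmnt*time / alpha=0.1 cl ddfm=kr"
- residual part: "repeated time / type=un subject=subject"
- random part: "random subject"

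The A-B differences "will be calculated and presented with the corresponding 90% CIs". For A-C, "The same model will be used to assess the impact of a single dose of lasmiditan 200 mg on the cardiovascular parameters of sumatriptan".

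The design gives reason to expect a subject's day to look alike from period to period. Protocol 7.2.1: "The doses will be administered at approximately the same time on Day 1 of each treatment period". Protocol 9.4.2.2: "Subjects will be encouraged to keep the same routine without strenuous activity during the ABPM recording days". Subjects stay in the unit until Day 3 of Period 4 (Protocol section 2) and are fed about 3 hours after dosing (Protocol 6.3.1).

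**The concern.** In a crossover, the gain at each hour comes from comparing a subject with himself at that same hour. One constant subject effect carries only his general level. It does not say that his 3-hour value in one period resembles his 3-hour value in another more than it resembles his other hours. If he has his own night dip or meal response, that pattern recurs in every period and cancels in his A-B or A-C difference at that hour. A model without a subject-by-time term, and with residuals independent between periods, treats the pattern as noise. The single predose baseline per period cannot remove it, because it is one number for all hours. The fixed time effect removes only the average profile.

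The hourly contrasts are the planned analysis that locates a transient rise in pressure or fall in pulse rate. Needlessly wide intervals there make it harder to say when an interaction is present or how large it could be.

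**Working it through.** **1. The plan's own precision figure.** Inputs from Protocol 10.1 and SAP 7: SD 12.7 mmHg for the within-subject change in SBP, 30 completers, 90% CI, 90% probability.

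- Expected half-width: t(0.95, 29) × 12.7/√30 = 1.699 × 2.319 = 3.94 mmHg.
- With 90% assurance: 3.94 × √(χ²(0.90, 29)/29) = 3.94 × 1.161 = 4.57, which rounds to the stated 4.6.
- Reading 12.7 as a per-period SD would give 6.47 instead. So 12.7 is the SD of a between-period difference, and the per-period residual variance is s_e² = 12.7²/2 = 80.6.

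**2. The code as written.** The residual block is the whole subject and its rows are indexed by time alone. Two records of one subject at the same hour in different periods map to the same row, so their residual correlation is 1. With 8 hours and 4 periods, the 32 × 32 covariance of a subject's records has rank 8, with or without the random subject effect. With 24 post-dose hours (assumed from the 24-hour recording), 96 records have rank at most 24. The likelihood is undefined, so there is no CI to assess.

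**3. After the usual repair (one residual block per subject-period).** Let R be the true within-period residual covariance and s_st the SD of a recurring subject-by-hour effect, independent between hours.

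- Within-subject contrasts, three per subject, estimate R.
- Subject means, multiplied by 4, estimate R + 4·s_st²·I, apart from the constant subject effect.
- Pooling 3:1 gives (3R + R + 4·s_st²·I)/4 = R + s_st²·I.

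The fitted hourly variance is therefore s_e² + s_st², while the A-B difference actually varies with s_e² only:

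width ratio = √(1 + s_st²/s_e²) = 1/√(1 − r), where r = s_st²/(s_st² + s_e²).

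The documents give no s_st, so the range is assumed:

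| s_st (mmHg) | r | Ratio, independent between hours | Excess if smooth over time | Expected half-width 3.94 becomes at most |
|---|---|---|---|---|
| 0 | 0 | 1.00 | 0% | 3.94 |
| 3 | 0.10 | √(1 + 9/80.6) = 1.05 | about 2-4% | 4.15 |
| 4.5 | 0.20 | √(1 + 20.25/80.6) = 1.12 | about 4-8% | 4.41 |
| 6 | 0.31 | √(1 + 36/80.6) = 1.20 | about 7-15% | 4.74 |

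The smooth column comes from large-sample likelihood fits with 8 hours and 4 periods. For example, a subject-by-hour variance of 20 with autocorrelation 0.7 between adjacent hours, against a residual of 80, gives ratios of 1.05 to 1.08 by hour. In that setting the independent case gives 1.10 to 1.11, slightly below the closed form. The excess is smaller for a smooth profile because the constant subject effect absorbs part of it.

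**4. Simulation.**

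- 32 subjects, 24 hours, AR(1) 0.5 residual, profile independent between hours, 150 runs per setting: SE ratios 0.996, 1.053, 1.112 and 1.202 for s_st = 0, 3, 4.5 and 6. Coverage of the nominal 90% CI was 91.7%, 92.6% and 95.2% for the last three. The SAP's primary-type model fitted hour by hour gave SE ratios of 0.995 to 0.998 and coverage of 89% to 90%.
- 32 subjects, 8 hours, subject-by-hour variance 20 against residual 80, 150 runs: coverage 0.94 (independent) and 0.92 (smooth). With cross-period covariance modelled it was 0.91 and 0.90.

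**The case against.** A reader might infer that the analysis as written makes the hourly CIs too wide. The documents do not support that. The written code over-ties the periods and yields no CI at all. The prose does not specify the residual covariance, and a residual structure over period and time, blocked by subject, would satisfy its wording and capture same-hour similarity. The widening belongs to one repair of the code. That stands, and the point is worded accordingly. The repair in question is nonetheless the usual one, and nothing in either document steers the analyst away from its cost.

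The size is also open to challenge. No subject-by-hour SD is given, the source study for 12.7 mmHg is redacted, and neither document says the figure describes hourly means. The mechanisms offered, a night dip and a meal response, are smooth over time, which favours the lower ranges. All of this stands: the larger percentages are upper values under an assumption.

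Finally, the consequence is limited. The SAP's primary peak/nadir analysis has one value per period and already pairs subjects correctly. The hourly estimates are not biased, the error is conservative, and no margin or decision rule rests on the hourly intervals. The 4.6 mmHg target is not stated for hourly contrasts. This also stands, and it limits the weight of the point. It does not remove the need to replace code that cannot run.

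**Conclusion.** The concern holds in conditional form. Both documents specify one constant subject effect and no subject-by-time term, and the SAP's example code is singular. Once the residual is blocked by subject-period, any recurring subject-specific hourly profile is counted as error, and Kenward-Roger degrees of freedom do not correct this. The hourly A-B and A-C 90% CIs are then conservative by the amounts in the table.

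Those amounts rest on three assumptions: a residual variance of 80.6 derived from the planning SD, an assumed subject-by-hour SD of 3 to 6 mmHg, and complete data over four periods. The excess varies by hour and is zero if no such profile exists. It would be wrong to read this as bias or as a flaw in the peak/nadir primary analysis. The change should be made, because the model must be respecified in any case and the better specification is already in the SAP.

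**What to change.** In SAP 9.4.2, obtain the hourly A-B and A-C estimates and 90% CIs by fitting the SAP's own primary-analysis model (baseline, treatment, period, sequence, random subject) separately to the change from baseline at each post-dose hour. This pairs each subject with himself at that hour, gives each hour its own period effect, and replaces the code that cannot be fitted. Record it in SAP section 11, which now declares no changes, as a change from Protocol 10.3.3.2.

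A joint model is acceptable only if it uses one residual block per subject-period, adds a random subject-by-time effect, and names a simpler residual structure in case the 24 × 24 unstructured matrix (24 × 25/2 = 300 parameters, with about 30 completers) does not converge.

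The cost is SAP wording and by-hour processing in the program, with no new data. The downside is that separate fits do not borrow information across hours when an hour is missing, which should matter little for inpatient monitoring.

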10.1. Sample Size Determination

Up to 40 subjects may be enrolled to ensure 30 subjects complete the study. Assuming standard deviation for the change, within-subject, in SBP of 12.7 mmHg (based on results from study), this will result in a 90% probability that the half-width of the 90% confidence interval (CI) about the mean within-subject change between periods is no larger than 4.6 mmHg.

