10.3.3.2. Statistical Inference of Cardiovascular Parameters

Cardiovascular parameters will be listed, and summarized using descriptive statistics, as appropriate.

Baseline value will be defined as the mean value during the 2 hours pre-dose for each period. Changes from baseline in cardiovascular parameters SBP, DBP, MAP, and PR will be analyzed to determine the impact of a single dose of sumatriptan 100 mg on the cardiovascular parameters

of lasmiditan. A repeated measures linear mixed-effects model with baseline as a covariate, fixed effects for time point, treatment, period (1, 2, 3, or 4), treatment sequence, and the treatment by time point interaction, and a random effect for subject will be used. Least squares (LS) means and treatment differences ([lasmiditan + sumatriptan] - [lasmiditan + placebo]) will be calculated and presented with the corresponding CIs. The same model will be used to assess the impact of a single dose of lasmiditan 200 mg on the cardiovascular parameters of sumatriptan.

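### Both cardiovascular models fit one baseline slope that mixes between- and within-subject variation, so A-B and A-C are adjusted inefficiently for chance differences in period baseline

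*SAP*

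**What the plan says.** SAP 9.4.1 makes baseline specific to the period: "Baseline value will be defined as the mean value during the 2 hours pre-dose for each period". Each subject can therefore contribute up to four baselines, which vary both between and within subjects.

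The primary model in SAP 9.4.2 is "model primcard = base trtmnt period seq / alpha=0.1 cl ddfm=kr", with a random subject effect. Its response is one value per subject and period: "where 'primcard' is the change from baseline in the peak/nadir hourly mean values of the primary cardiovascular parameters". The repeated-measures model is "model cardio = base time trtmnt period seq trtmnt*time / alpha=0.1 cl ddfm=kr", also with a random subject effect, and with the covariance statement "repeated time / type=un subject=subject".

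The code is labelled an example, but the SAP prose lists the same effects. For the repeated-measures model so does Protocol 10.3.3.2: "A repeated measures linear mixed-effects model with baseline as a covariate, fixed effects for time point, treatment", where the only interaction with time is that of treatment. The comparison A-C follows suit: "The same model will be used to assess the impact of a single dose of lasmiditan 200 mg on the cardiovascular parameters of sumatriptan". Likewise, a parallel sentence covers the primary analysis.

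Neither model has a term for the subject's mean baseline. The repeated-measures model has no baseline-by-time term. The documents give no reason for a common slope and plan no sensitivity analysis of it.

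**The concern.** A-B and A-C are within-subject contrasts. If a subject happens to start the A period 3 mmHg above the B period, the right amount to remove is 3 times the within-subject slope. How subjects differ from one another in their usual pressure has no bearing on it. A stable personal level makes the between-subject slope high. Day-to-day fluctuation, and a baseline of only about six readings (Protocol 9.4.2.2: one every 20 minutes over 2 hours), pull the within-subject slope down. A single coefficient has to compromise between the two. Analysing change from baseline does not help, because with baseline in the model it only moves the coefficient by 1.

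At stake is precision, which is the only criterion on which the trial is sized, together with a conditional error in A-B proportional to whatever baseline imbalance happens to arise between the two periods.

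**Working it through.** **The plan's own figure.** Protocol 10.1 and SAP 7 give 30 completers and a 90% CI half-width of at most 4.6 mmHg with 90% probability: "Assuming standard deviation for the change, within-subject, in SBP of 12.7 mmHg". Taking 12.7 as the SD of a between-period difference:

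half-width = t(0.95; 29) × 12.7 × √(χ²(0.90; 29)/29) / √30 = 1.699 × 12.7 × √(39.09/29) / 5.477 = 4.57 mmHg.

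The figure reproduces; the probability of 4.6 or less is 0.908. It uses no baseline slope, so this point leaves it unchanged.

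**Why the slope is a mix.** With complete data and four periods, setting aside the other fixed effects, the fitted slope is

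β = (w_W β_W + w_B β_B)/(w_W + w_B), with w_W = SS_within/σ²_e and w_B = SS_between/(σ²_e + 4σ²_s).

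Here σ²_e is the residual variance and σ²_s the subject variance. β equals β_W only if the two slopes agree or w_B is zero.

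**Size of the consequence.** Let d = β − β_W, let s be the within-subject SD of baseline, and let v be the per-period residual variance, taken as 12.7²/2 = 80.6.

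- SD of the mean A-B baseline imbalance: s√(2/30).
- Shift in A-B at a 1-SD imbalance: d × s√(2/30).
- CI widening: √(1 + d²s²/v) − 1.

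Example with s = 7 and d = 0.3: imbalance SD 1.81, shift 0.54 mmHg, widening √(1 + 0.09 × 49/80.6) − 1 = 2.7%. Over s = 5 to 9 and d = 0.1 to 0.5, the shift runs from 0.1 to 1.2 mmHg and the widening from 0.2% to 12%. Both ranges of s and d are assumptions.

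**Primary model, simulated** (four sequences, 32 subjects, REML with random subject; all variance components assumed):

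- Eight scenarios with between-subject baseline SD 9 to 12 and within-subject SD 4 to 8. In the reference case the planned slope was −0.30 against a within-subject −0.56 on the change scale, or 0.70 against 0.44 on the raw scale. Variance ratios (planned to split) were 0.996 to 1.069. The square roots give no gain in one scenario and 0.8% to 3.4% of CI width in the other seven. A-B moved by a median of 0.1 to 0.4 mmHg (95th percentile 0.3 to 1.4).
- A second set, with between-subject SD 9, a day-level process of SD 6 decaying over 2, 6 or 24 h, and hourly noise SD 4, not rescaled to 12.7. Raw slope 0.25 to 0.80 against 0.05 to 0.60 within subject; CI 4 to 6% wider. The shift was 0.20 to 0.26 mmHg per mmHg of imbalance. With imbalance SD 1.6 to 1.9 that is 0.20 × 1.6 = 0.3 to 0.26 × 1.9 = 0.5 mmHg. Mean bias was about 0 and coverage 0.89 to 0.92.
- A further set gave 0.25 to 0.83 against 0.05 to 0.50, and a CI 4 to 16% wider.

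**Repeated-measures model, simulated** (the second set's components plus a day-constant SD of 3, scaled so that the between-period SD averages 12.7; 250 runs per scenario). The fixed model has both baseline components by time.

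| Decay time | Fitted common slope | True within slope, h 1 / h 24 | SE at h 1, planned v fixed | SE at h 24, planned v fixed |
|---|---|---|---|---|
| 2 h | 0.55 | 0.58 / 0.20 | 1.70 v 1.69 | 2.04 v 1.92 (+6%) |
| 6 h | 0.74 | 0.74 / 0.19 | 1.50 v 1.49 | 2.24 v 1.99 (+13%) |
| 24 h | 0.85 | 0.82 / 0.42 | 1.62 v 1.61 | 2.50 v 2.29 (+9%) |

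Pooling lifts the common slope to about the hour-1 value, so hour 1 loses about 1% or less and hours 2 to 4 lose 0 to 4%. By empirical SD the hour-24 loss was 4%, 11% and 4%. The shift at hour 24 was 0.31 to 0.60 mmHg per mmHg of imbalance, or 0.5 to 1.1 mmHg at 1 SD. Coverage was 0.87 to 0.94. Splitting the slope while keeping it constant over time raised the hour-1 SD by 1 to 7% relative to the fixed model.

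These runs used an unstructured block per subject and period. The example code blocks by subject alone, which repeats each time level four times within a block. That is a separate matter, but it means the runs are not of the code exactly as printed.

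**The case against.** The strongest reply is that nothing here is invalid. Baseline precedes dosing in a randomised crossover, the covariate was prespecified in the protocol, the 4.6 mmHg target does not depend on it, and every magnitude rests on variances that the documents do not supply. Hourly values and interval means are summarised descriptively in any case (SAP 9.4.1), and SAP 3 allows supplementary analyses. All of that stands. It limits the point to efficiency, but it is no reason to keep the less efficient adjustment when the primary-model change costs one parameter.

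A second reply concerns cost, and it also stands. With 24 hourly levels, two baseline components by time need 48 parameters in place of 1, so 47 more, with about 30 completers and an unstructured covariance.

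A reader might infer that the harm lies in the early hours, since a pre-dose mean predicts those best and lasmiditan peaks at 1 to 2.5 h (Protocol 3.2). A calculation that leaves out between-subject pooling does show 3 to 20% extra variance at hour 1 in most cases. The SAP's random-subject model does pool, however. Over a grid of assumed values, pooling cut the median hour-1 variance inflation from 6.5% to 2.4% (interquartile range 0.5 to 5.6%), while hour 24 rose to a median of 12%. Some extreme combinations still cost hour 1 a good deal, so an early loss cannot be excluded, but it is not the general result.

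**Conclusion.** The point holds as one of efficiency. In both models the coefficient used to adjust A-B and A-C is not the within-subject one. For the primary analysis the 90% CI is about 1 to 6% wider than needed in most assumed scenarios, with the exceptions shown, and the typical shift of 0.1 to 0.5 mmHg is small against a planned half-width of 4.6 mmHg. In the repeated-measures analysis the cost is mainly late.

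Two stronger readings are not supported. One is that A-B is biased or its interval invalid: the error is conditional on a random imbalance and averages to about zero. The other is that both models impose one slope across 24 hours: the primary model has one peak or nadir value per period and no time factor, so this applies only to the repeated-measures model.

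The direction follows from the model specification whenever the two slopes differ. The sizes depend on the assumed variance components and decay times. This is a cheap improvement, worth making for the primary model above all.

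**What to change.** In SAP 9.4.2 derive two variables per subject and parameter: `base_mean`, the mean of the subject's available period baselines, and `base_dev`, the period baseline minus `base_mean`.

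- **Primary model:** `model primcard = base_dev base_mean trtmnt period seq`. Cost: one extra parameter and no new data. Keeping `base` and adding `base_mean` gives the same fit.
- **Repeated-measures model:** add `base_mean` together with a baseline-by-time interaction for both components, not the split alone, given the hour-1 loss shown above. State the cost of about 47 extra parameters if time has 24 hourly levels. A leaner form lets each slope vary over the intervals already planned in SAP 9.4.1 (0-4, 4-8, 8-12 and 12-24 h): 2 × 4 = 8 parameters in place of 1, so 7 extra.

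Keep the LS means, contrasts and 90% CIs as planned. Record the change in SAP 11, which at present declares no departures from the protocol, and make it before the sign-off that SAP 3 requires ahead of first dosing. If the sponsor prefers the common slope, the SAP should say why.

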3. INTRODUCTION

This SAP has been developed after review of the Clinical Study Protocol (final version dated 17 August 2017) and Protocol Amendment (c) (final version dated 20 October 2017).

This SAP describes the planned analysis of the safety, tolerability and pharmacokinetic (PK) data from this study. A detailed description of the planned TFLs to be presented in the clinical study report (CSR) is provided in the accompanying TFL shell document.

The intent of this document is to provide guidance for the statistical and PK analyses of data. In general, the analyses are based on information from the protocol, unless they have been modified by agreement between Eli Lilly and Company and Covance Early Clinical (EC) Biometrics. A limited amount of information concerning this study (e.g., objectives, study design) is given to help the reader's interpretation. This SAP must be signed off prior to first subject administration for this study. When the SAP and TFL shells are agreed upon and finalized, they will serve as the template for this study's CSR.

This SAP supersedes the statistical considerations identified in the protocol; where considerations are substantially different, they will be so identified. If additional analyses are required to supplement the planned analyses described in this SAP, they may be performed and will be identified in the CSR. Any substantial deviations from this SAP will be agreed upon between Eli Lilly and Company and Covance EC Biometrics and identified in the CSR. Any minor deviations from the TFLs may not be documented in the CSR.

This SAP is written with consideration of the recommendations outlined in the International Council on Harmonisation (ICH) E9 Guideline entitled Guidance for Industry: Statistical Principles for Clinical Trials¹ and the ICH E3 Guideline entitled Guidance for Industry: Structure and Content of Clinical Study Reports².

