5. STUDY DESIGN

This is a randomized, double-blind, crossover study with 4 study periods in healthy subjects. All subjects will participate in 4 treatment periods. The treatments are as follows:

- Treatment A: lasmiditan 200 mg + sumatriptan 100 mg
- Treatment B: lasmiditan 200 mg + placebo
- Treatment C: sumatriptan 100 mg + placebo
- Treatment D: placebo + placebo

Each subject will be randomized to one of 4 treatment sequences in a William's square design as outlined in Table 1.

Table 1. Sequences in Study LAHU

Sequence	Period 1	Period 2	Period 3	Period 4
1	Lasmiditan + sumatriptan	Lasmiditan + placebo	Sumatriptan + placebo	Placebo + placebo
2	Lasmiditan + placebo	Sumatriptan + placebo	Placebo + placebo	Lasmiditan + sumatriptan
3	Sumatriptan + placebo	Placebo + placebo	Lasmiditan + sumatriptan	Lasmiditan + placebo
4	Placebo + placebo	Lasmiditan + sumatriptan	Lasmiditan + placebo	Sumatriptan + placebo

Screening Period:

All subjects will participate in a screening visit up to 28 days prior to Period 1 study drug dosing.

Treatment Periods:

All subjects will participate in 4 treatment periods. Subjects will be randomized to one of 4 treatment sequences. They will be admitted to the clinical research unit (CRU) the day prior to dosing (Day -1) in Period 1, and will be dosed on Day 1 of each treatment period according to their assigned treatment sequence (Table 1). Subjects will be discharged from the CRU on Day 3 of Period 4 following the collection of all ambulatory blood pressure (ABP) measurements and PK blood samples.

There will be a washout of at least 4 days between each dosing day.

All subjects will be discharged from the study at least 5 days after discharge from Period 4.

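### The SAP's repeated-measures code takes the whole subject, not the subject-period, as its residual block, so the hour-by-hour blood pressure and pulse model cannot be fitted as written

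*SAP*

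**What the plan says.** SAP section 5 describes the design: "This is a randomized, double-blind, crossover study with 4 study periods in healthy subjects". Section 9.4.1 derives hourly means of SBP, DBP, MAP and PR, so each subject contributes the same set of hours in each of four periods.

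Section 9.4.2 has two inferential models. The first, labelled primary, analyses one peak or nadir value per subject-period and has no REPEATED statement. The second is the repeated measures analysis over time points. Its fixed part is "model cardio = base time trtmnt period seq trtmnt*time / alpha=0.1 cl ddfm=kr". Its covariance comes from two statements, "repeated time / type=un subject=subject" and "random subject". Treatment differences by hour are requested with "lsmeans trtmnt*time / alpha=0.1 cl pdiff". The section then extends the model to the other comparison: "The same model will be used to assess the impact of a single dose of lasmiditan 200 mg on the cardiovascular parameters of sumatriptan".

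Protocol section 10.3.3.2 describes the same time-course model in words, beginning "A repeated measures linear mixed-effects model with baseline as a covariate, fixed effects for time point, treatment, period (1, 2, 3, or 4), treatment sequence". Neither the protocol text nor the SAP text names a residual block or a covariance structure. The REPEATED line is therefore the only place where the residual covariance is specified.

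**The concern.** In a crossover with repeated measurements inside each period, residuals are correlated across hours within one subject's period. Periods of the same subject are linked through the subject effect. The code instead makes the subject the residual block and indexes it by hour only. Period enters as a fixed effect but appears in neither the block nor the repeated effect. Two records of one subject at hour 3, one on the combination and one on lasmiditan alone, are then treated as carrying the same residual.

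This model supplies the by-hour treatment differences with 90% confidence intervals for SBP, DBP, MAP and PR, for the combination against each single drug. The interval means (0-4 h and so on) in SAP 9.4.1 are descriptive only. If the model cannot be fitted, the plan has no hour-by-hour inference, and it does not say what would replace it.

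**Working it through.** **Plan's own figure.** No figure in the plan depends on this line. The sample size statement (SAP section 7: SD 12.7 mmHg, 30 completers) does reproduce: t(0.95, 29) x 12.7 x sqrt(chi-square(0.90, 29)/29)/sqrt(30) = 4.57, which rounds to the stated 4.6 mmHg. It does not use the time-course model.

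**Inputs.**
- Periods per subject, P = 4 (SAP section 5).
- Time points per period, T = 24. This is an assumption from hourly means over 24-hour ABPM; the SAP does not define the time points for this model. T = 12 and T = 4 were also checked.
- U: any positive-definite T x T matrix of covariances between hours.
- c: the random subject variance.
- Completers 30, enrolled up to 40 (SAP section 7).

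**Step 1: covariance as coded.** Two residuals of one subject have covariance U[hour i, hour j] whatever their periods. With J the all-ones matrix:

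R = J_P ⊗ U

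V = R + cJ = J_P ⊗ (U + cJ_T)

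J_P has rank 1, so V has rank T out of P x T, for any U and any c.

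**Step 2: smallest case.** Take one hour and two periods, with residual variance u.
- As coded, all four entries of V equal u + c, so the determinant is (u + c)² − (u + c)² = 0.
- With subject-by-period blocks, the diagonal is u + c and the off-diagonal is c, so the determinant is (u + c)² − c² = u(u + 2c) > 0.

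**Step 3: ranks.**

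| Setting | Size of V | Rank as coded | Rank with `subject*period` |
|---|---|---|---|
| T = 24, four periods | 96 | 24 | 96 |
| T = 24, two treatments only | 48 | 24 | 48 |
| T = 12, four periods | 48 | 12 | 48 |
| T = 4, four periods | 16 | 4 | 16 |

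The ranks were computed numerically, except the 48 of 48 at T = 12 for the corrected block, which follows from the algebra. Restricting the data to the two treatments being compared does not help.

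**Step 4: the contrast of interest.** For two records of one subject at hour t in different periods, the subject effect cancels.
- As coded, the variance of the difference is U_tt + U_tt − 2U_tt = 0.
- With the corrected block it is 2U_tt.

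**Step 5: likelihood.** REML needs the inverse and the log-determinant of V, and a singular V has neither. In a simulated trial of 30 subjects, four sequences, four periods and T = 4, the REML likelihood was undefined at the start value and at all 500 random parameter values. With the corrected block the same data gave a finite optimum, with the subject variance estimated separately from U.

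**Step 6: possible rescues.**
- Missing readings: V is singular as soon as one subject has the same hour recorded in two periods, so no realistic amount of missing data removes the problem.
- Numbering time uniquely over periods: this gives 96 levels and 96 x 97/2 = 4,656 covariance parameters from 30 to 40 subjects. It also confounds time with period and removes the comparison at a common hour.

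**Step 7: size of the unstructured matrix after correction.** It has 24 x 25/2 = 300 parameters. Subject-periods number 30 x 4 = 120 or 40 x 4 = 160. At 120 there are up to 120 x 24 = 2,880 values, or 2,880/300 = 9.6 per parameter.

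PROC MIXED itself was not run. The result rests on the algebra, the matrix ranks and the direct likelihood evaluation.

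**The case against.** The strongest reply concerns weight, not algebra. The line is introduced as example code with a placeholder data set, and the prose model does not state a subject-wide block. Because the likelihood is undefined, no wrong estimate or interval could come out of it; a programmer would have to correct the block before any output existed. SAP section 3 lets substantial deviations be agreed and reported in the CSR. The SAP supersedes the protocol's statistical section and makes peak/nadir the primary analysis, so the affected model is supportive. Finally, a large unstructured matrix does not by itself imply non-convergence.

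Much of this stands. The failure is visible, the primary analysis is intact, and the need for a fallback structure does not follow from the defect: 120 blocks exceed the matrix dimension of 24, and at T = 4 the matrix would have only 10 parameters. The fallback list is separate, sensible advice.

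The example label does not remove the point. The SAP presents the code as what will be run, and no other text specifies the residual covariance. If the line is discounted, the covariance is not pre-specified at all.

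**Conclusion.** The repeated-measures code is wrong as written. For any number of time points and any covariance values, V is singular once a subject has the same hour in more than one period: rank 24 of 96 at 24 hours, with zero implied variance for same-hour treatment differences. The general result needs only that time is coded as hour after dosing; the 24 is an assumption that sets the size, not the conclusion.

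The damage is limited to the time-course model: hourly differences for SBP, DBP, MAP and PR in both comparisons. The peak/nadir analysis has four records per subject, one per period, and its covariance matrix has full rank. This should be fixed, but it does not threaten the trial's primary result. The practical loss is pre-specification, which the SAP itself aims to protect: "This SAP must be signed off prior to first subject administration for this study".

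**What to change.** In the REPEATED statement of the time-course code, change the `subject=` option from `subject` to `subject*period`, and keep the random subject effect. Add one sentence to the model text saying that the residual covariance is across time points within a subject-period. It is also worth adding a second sentence with an ordered list of fallback covariance structures, on the same block, for use if the unstructured matrix does not converge; the order is the sponsor's choice.

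The cost is one line of code and two sentences. Data collection, the sample size and the primary analysis do not change. Making the change before SAP sign-off keeps the covariance model fixed in advance.
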